### **3.2.2 Secondary Objectives**

- To assess median progression free survival. This will be assessed via the Response Evaluation Criteria in Solid Tumors (RECIST) version 1.1 guidelines after every 3 cycles (9 weeks) of therapy].
- To assess median overall survival from the date of enrollment to the time of death will be documented.
- To assess the objective response rate as measured by RECIST v 1.1.
- To assess the toxicity of dose regimen using the CTEP NCI Common Terminology Criteria for Adverse Events (CTCAE Version 4.0).

## **3.3 Tertiary Objectives of phase 1 and 2**

- Measurement of circulating angiogenic cytokines (CAFs): VEGF, sVEGFR 1/2, PlGF, GMCSF, Leptin, IL-1a, IL-8, IL-6, FGFb, Osteopontin and Pentraxin-3.
- Measurement of drug levels and PK/PD modeling

## **4 METHODOLOGY**

### **4.1 Study Design**

This is an open-label, non-randomized, multicenter, Phase I/II study of nintedanib and capecitabine in patients with metastatic colorectal cancer refractory to irinotecan and oxaliplatin based therapy. The study will include a Phase I dose-finding portion, followed by a non-randomized Phase II component. Nintedanib and capecitabine are both oral formulations, to be taken twice daily as prescribed in the present study. Nintedanib will be administered at a fixed dose as dictated in the protocol. The total daily dose of capecitabine will be calculated based upon actual body weight and split into two comparable portions, and doses of both drugs are to be self-administered approximately 12 hours apart (+/- 2 hours), within 30 minutes of a meal. For the purposes of this study, a cycle will be defined as 3 weeks (i.e., 21 days). Nintedanib is to be self-administered twice daily for 21 days (i.e., 1 complete cycle), while capecitabine will be dosed cyclically, in a 2 weeks on / 1 week off fashion. Disease assessment will occur after every three cycles of therapy (9 weeks). For the Phase I study, patients will be evaluated for toxicity on days 1 and 8 of the first two cycles. Otherwise, all patients will be evaluated on day one of each cycle of therapy. Treatment will continue until disease progression, in the absence of undue toxicity.

#### 4.1.1 Phase I

A small initial Phase I lead-in will be conducted, utilizing a 3+3 design to determine the recommended phase II dose (RP2D). The Phase I portion provides limited toxicity information about the combination therapy in refractory metastatic colorectal cancer patients. The maximum tolerated (or administered) dose level from the Phase I will be utilized as the recommended Phase 2 dose. Two dose levels are planned, with dose level 2 expected to be the RP2D. Full details including the initial dosing strategies and dose escalation schema are present in **Section 6**.

#### 4.1.2 Phase II

The RP2D from the Phase I study has been determined to be dose level 2. There is no formal interim analysis planned or early stopping rules. However, toxicity and safety outcomes will be regularly reviewed.

#### 4.1.3 Correlative Studies

For both the Phase I and Phase II study, correlative blood will be drawn at baseline, cycle 1 day 15, and cycle 3 day 1 for analysis of a panel of cytokines and growth factors (see below), to be correlated to PK data, for a select biomarker panel and outcomes. This will be performed only on the 1st 32 patients enrolled in the study only. Following administration of both nintedanib (BIBF1120) and capecitabine, PK samples for nintedanib will be collected on Day 1, Cycle 1 at pre-dose, and at 0.5-1 hr, 2-4 hr, 5-6 hr, and 6-8 hr post dose and Day 2 (trough level). In addition, PK samples will be collected on Day 15 at predose, 2-4 hr post-dose, and 5-6 hr post-dose (**Section 8.10**). Circulating angiogenic cytokines (CAFs) will additionally be analyzed via blood collection on Day 1, Cycle 1 at pre-dose and 2-4 hr post-dose, on Day 15 2-4 hr post-dose and on Day 1, Cycle 3, 2-4 hr post-dose. Details of collection and timing are summarized in **Section 8.11**.

All participants will sign an informed consent prior to study related tests. All participants will meet the inclusion and exclusion criteria summarized in **Section 5.1** and **Section 5.2**. Participants will be treated on an outpatient basis.

#### 4.2 Target Accrual and Study Duration

It is expected that a total of 9 patients will be enrolled at two dose levels in the Phase I portion, with potential for a maximum of 18 patients. The number of participants required is a function of the unknown dose-toxicity relationship. Patients treated at the RP2D (n=6) will be included in the Phase II study analysis. Up to an additional 30 patients will be enrolled in the Phase II portion of the study, for a Phase II sample size of 36. Summarily, the study is expected to accrue 39 patients (9 + 36 - 6). However, if toxicity is greater than expected, a maximum of 48 patients might be required (18 + 36 - 6). Enrollment is expected to be split between the two sites involved: Roswell Park Cancer Institute and City of Hope. Thus, in the case of 39 patients being enrolled, it is anticipated that approximately 20 patients would be enrolled at RPCI and 19 at City of Hope. Accrual is expected to take up to 2 years. Median PFS has historically stood at approximately 2 months and this study aims to provide a PFS rate at 18 weeks (~4 months) of 40%. It is anticipated that patients will be on study for approximately 18 weeks.

## 5 PARTICIPANT SELECTION

### 5.1 Inclusion Criteria

To be included in this study, participants must meet the following criteria:

1. Age  $\geq$  18 years of age.
2. Have an ECOG Performance Status of 0 – 1. Refer to **Appendix B**.
3. Have the following clinical laboratory values:
  - Hemoglobin  $\geq$  9 g/ dL
  - Absolute neutrophil count  $\geq$  1500/ mm^3
  - Platelet count  $\geq$  100,000/ mm^3
  - Creatinine  $\leq$  1.5 ULN AND CrCl  $>$  50 mL/min by Cockcroft-Gault equation:
    - Males =  $(140 - \text{age [yrs]})(\text{Body weight [kg]})(72)(\text{serum creatinine [mg/dL]})$
    - Females =  $0.85 * (140 - \text{age [yrs]})(\text{Body weight [kg]})(72)(\text{serum creatinine [mg/dL]})$
  - Bilirubin  $\leq$  ULN
  - AST / ALT  $\leq$  1.5 ULN if without liver metastases
  - AST/ ALT  $\leq$  2.5 x ULN if with liver metastases
  - Coagulation parameters: International normalized ratio (INR)  $\leq$  2, prothrombin time (PT) and partial thromboplastin time (PTT)  $<$  1.5 X institutional ULN
4. Have measurable disease per RECIST 1.1 criteria.
5. Histologically or cytologically proven adenocarcinoma of the colon or rectum.
6. Prior progression following a fluoropyrimidine-based therapy and progression following or intolerance to irinotecan and oxaliplatin, as well as anti-EGFR therapy (e.g., panitumumab or cetuximab) for RAS wild-type patients.
7. Ability to swallow and retain oral medication.
8. Participants of child-bearing potential must agree to use adequate contraceptive methods (e.g., hormonal or barrier method of birth control; abstinence) prior to study entry and for three months following completion of therapy. Should a woman become pregnant or suspect she is pregnant while she or her partner is participating in this study, she should inform her treating physician immediately.
9. Participant or legal representative must understand the investigational nature of this study and sign an Independent Ethics Committee/Institutional Review Board approved written informed consent form prior to receiving any study related procedure.

## 5.2 Exclusion Criteria

Participants will be excluded from this study for the following:

1. Prior treatment with nintedanib.
2. Prior treatment with regorafenib.
3. Major injuries or surgery within the 4 weeks prior to initiation of therapy with incomplete wound healing or planned surgery during the on-study treatment period.
4. Uncontrolled hypertension: systolic blood pressure  $\geq 160$ , diastolic blood pressure  $\geq 90$ .
5. Urine Protein/creatinine ratio  $\geq 1.0$ . Refer to **Appendix E**.
6. History of clinically significant hemorrhagic or thrombotic event within the past 6 months, not including uncomplicated catheter-associated venous thrombosis. Patients on anti-coagulation are not permitted to be on any oral formulations (warfarin, rivaroxaban, dabigatran, etc.) due to concern for drug-drug interaction.
7. Unstable angina, symptomatic congestive heart failure or cardiac arrhythmia requiring anti-arrhythmic therapy (Beta-blockers, calcium channel blockers and digoxin are allowed).
8. History of cerebrovascular or myocardial ischemia within 6 months of initiation.
9. Known inherited predisposition to bleeding or thrombosis.
10. Known active or chronic hepatitis B or C or HIV.
11. Untreated brain metastases.
12. History of second primary malignancy diagnosed within 3 years prior to enrollment, excluding:
  - a. *In-situ* cervical carcinoma
  - b. Superficial bladder cancer
  - c. Non-melanoma skin cancer
  - d. Stage I breast cancer
  - e. Low grade (Gleason  $\leq 6$ ) localized prostate cancer
  - f. Any additional malignancy which has been in clinical remission for at least 1 year.
13. Pregnant or nursing female participants.
14. Unwilling or unable to follow protocol requirements.
15. Any condition which in the Investigator's opinion deems the participant an unsuitable candidate to receive study drug.
16. Received an investigational agent within 4 weeks prior to enrollment.
17. **Phase I:** History of intolerance to capecitabine at doses  $\leq 1000$  mg/m^2 BID, as defined by documented  $\geq$  grade 3 hand-foot syndrome; documented severe diarrhea requiring hospitalization; or other documented severe AEs attributable to capecitabine.

18. **Phase II:** History of intolerance to capecitabine at doses below 1000 mg/m^2 BID, as defined by documented  $\geq$  grade 3 hand-foot syndrome; documented severe diarrhea requiring hospitalization; or other documented severe AEs attributable to capecitabine.

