|  |  |  | 10. Known active or chronic hepatitis B or C, or HIV   |      |
|  |  |  | 11. Untreated brain metastases.  |      |
|  |  |  | 12. History of second primary malignancy diagnosed within 3 years prior to enrollment, excluding: 
 
a. In-situ cervical carcinoma
 
b. Superficial bladder cancer
 
c. Non-melanoma skin cancer
 
d. Stage I breast cancer
 
   |      |

| EXCLUSION CRITERIA       |                          |                          |   |      |
|--------------------------|--------------------------|--------------------------|---|------|
| Yes                      | No                       | N/A                      | All answers must be "No" or "N/A" for participant enrollment.   | Date |
|                          |                          |                          | e. Low grade (Gleason $\leq$ 6) localized prostate cancer
f. Any additional malignancy which has been in clinical remission for at least 1 year.   |      |
|  |  |  | 13. Pregnant or nursing female participants.  |      |
|  |  |  | 14. Unwilling or unable to follow protocol requirements.  |      |
|  |  |  | 15. Any condition which in the Investigator's opinion deems the participant an unsuitable candidate to receive study drug.  |      |
|  |  |  | 16. Received an investigational agent within 4 weeks prior to enrollment  |      |
|  |  |  | 17. Phase I: History of intolerance to capecitabine at doses $\leq$ 1000 mg/m  BID, as defined by documented $\geq$ grade 3 hand-foot syndrome, documented severe diarrhea requiring hospitalization, or other documented severe AEs attributable to capecitabine  |      |

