|  |  |  | 18. Phase II: History of intolerance to capecitabine at doses below 1000 mg/m  BID, as defined by documented $\geq$ grade 3 hand-foot syndrome; documented severe diarrhea requiring hospitalization; or other documented severe AEs attributable to capecitabine. |      |

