**Table 2 Available Dose Levels**

| Dose level | Capecitabine a                                 | Nintedanib b |
|------------|---|-------------------------|
| -1         | 1500 mg/m  PO daily
(in two divided doses) | 150 mg PO bid           |
| 1          | 2000 mg/m  PO daily                           | 150 mg PO bid           |

|   |   |               |
|---|---|---------------|
|   | (in two divided doses)                                    |               |
| 2 | 2000 mg/m  PO daily
(in two divided doses) | 200 mg PO bid |

a Capecitabine will be taken only on the first 14 days (followed by 7 days off) of the 21 day cycle.

b Nintedanib will be taken for the complete 21 day cycle.

Dose escalation will proceed in a 3+3 fashion. Standard 3+3 rules will be followed until the maximum tolerated (or administered) dose is found. Initially, 3 patients are enrolled at dose level 1. If no dose limiting toxicities (DLTs) are observed, then 3 new patients are escalated to dose level 2. If  $\geq 2$  DLTs are observed, then 3 new patients are de-escalated to dose level -1. If 1 DLT is observed, then an additional 3 patients are enrolled at dose level 1. In those 6 patients at dose level 1, if  $\leq 1$  DLTs are observed we proceed to dose level 2; otherwise we proceed to dose level -1. The same basic principles are followed until the Phase II recommended dose is identified. Planned dose escalation will proceed according to **Table 3**.

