**Table 3 Dose Escalation Scheme**

| Number of Participants with a Dose-Limiting Toxicity at a Given Dose Level    | Escalation Decision Rule  |
|---|---|
| 0 out of 3  | Enter 3 participants at the next dose level.  |
| $\geq 2$  | Dose escalation will be stopped. This dose level will be declared the maximally administered dose (highest dose administered). Three additional participants will be entered at the next lowest dose level if only 3 participants were treated previously at that dose.   |
| 1 out of 3  | Enter at least 3 more participants at this dose level. If 0 of these 3 participants experience a dose-limiting toxicity, proceed to the next dose level. If 1 or more of this group suffer a dose-limiting toxicity, then dose escalation is stopped, and this dose is declared the maximally administered dose. Three additional participants will be entered at the next lowest dose level if only 3 participants were treated previously at that dose. |
| $\leq 1$ out of 6 at highest dose level below the maximally administered dose | This is generally the recommended Phase 2 dose. At least 6 participants must be entered at the recommended Phase 2 dose.  |

The recommended Phase 2 dose will be considered tolerable if DLT(s) are observed in at most 1 of 6 patients completing at least 1 treatment cycle at that dose level. Available toxicity information about these drugs suggests that Dose Level 2 will be the recommended Phase 2 dose, and that 9 patients will be required for the Phase 1. Dose escalation will not proceed beyond dose level 2.

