### Phase II

- Nintedanib – treatment will be initiated at the RP2D orally twice daily, administered in a continuous fashion.
- Capecitabine – treatment will be initiated at the RP2D orally twice daily, taken for 14 days, followed by a 7 day break.

As in the Phase I study, therapy will be administered in 3 week cycles. Treatment will continue until progression, undue toxicity or at the physician/patient discretion. The primary endpoint is the PFS rate, defined as the proportion of patients who survive without disease progression (per RECIST criteria) for at least 18 weeks after the start of treatment. The 6 patients in Phase 1 patients treated at the recommended Phase 2 dose will be included in Stage 1 of the Phase 2 study. As of 1/29/16, dose level 2 has been determined to be the RP2D.

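### Exclusion 18 admits to Phase II a patient with documented severe capecitabine intolerance at exactly 1000 mg/m² BID, the Phase II starting dose, with no reason and no reduced start given

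*Combined protocol and SAP*

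**What the plan says.** Two numbered exclusions deal with earlier capecitabine intolerance, one for each phase. They define intolerance in the same way: documented hand-foot syndrome of grade 3 or higher, severe diarrhea that led to hospitalization, or another documented severe event attributed to capecitabine. They differ only in the dose threshold.

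- Phase I, exclusion 17 (eligibility form wording): "History of intolerance to capecitabine at doses $\leq$ 1000" mg/m² BID. Section 5.2 has the same threshold.
- Phase II, exclusion 18 (section 5.2): "History of intolerance to capecitabine at doses below 1000" mg/m² BID. The eligibility form repeats it.

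On dosing, section 6.2 says for Phase II: "Capecitabine – treatment will be initiated at the RP2D orally twice daily, taken for 14 days, followed by a 7 day break". It adds: "As of 1/29/16, dose level 2 has been determined to be the RP2D". Table 2 lists dose level 2 as capecitabine 2000 mg/m² daily in two divided doses with nintedanib 200 mg BID. No section gives a lower individual start to a patient with an intolerance history.

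On tolerability, section 6.2 states: "The recommended Phase 2 dose will be considered tolerable if DLT(s) are observed in at most 1 of 6 patients" who complete at least one cycle at that dose. On accrual, section 4.2 states: "Up to an additional 30 patients will be enrolled in the Phase II portion of the study".

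**The concern.** A threshold for earlier intolerance should normally keep out patients who have already failed the dose they are about to receive. Exclusion 17 does this. Exclusion 18 does it for every dose below the starting dose but not for the starting dose itself.

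That value is not a remote one. Section 2 describes 1000 mg/m² as the dose most often used in the US, and inclusion 6 requires progression after a fluoropyrimidine regimen, though not necessarily capecitabine.

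At stake is the safety of the individual patient. The clearest case is someone hospitalized for severe diarrhea at 1000 mg/m² BID. Section 1.8.2 expects some overlap in gastrointestinal and liver toxicity between the two drugs and says diarrhea may become more frequent with the combination. Phase I offers no reassurance for this history, because under exclusion 17 as written none of the six patients treated at the recommended Phase II dose could have had it.

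**Working it through.** There is no planned figure to reproduce. The check compares the two thresholds with the starting dose.

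**Inputs.** Capecitabine at dose level 2: 2000 mg/m²/day in two doses (Table 2). Phase II start: dose level 2 (section 6.2). Thresholds: ≤1000 mg/m² BID in Phase I and below 1000 mg/m² BID in Phase II (section 5.2, nos. 17 and 18). Approved dose: 1250 mg/m² BID (section 2). Phase II size: 36, of whom 6 come from Phase I and up to 30 are new (section 4.2).

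**Step 1, starting dose.** 2000 / 2 = 1000 mg/m² BID.

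**Step 2, apply each threshold.**

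| Dose not tolerated (mg/m² BID) | Phase I, no. 17 (≤1000) | Phase II, no. 18 (<1000) | Start as share of that dose |
|---|---|---|---|
| Below 1000 | Excluded | Excluded | Not applicable |
| Exactly 1000 | Excluded | Not excluded | 1000/1000 = 100% |
| 1250 | Not excluded | Not excluded | 1000/1250 = 80% |

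The rules differ at one value, and that value is the starting dose. A patient intolerant at 1250 enters either phase 20% below the failed dose. A patient intolerant at 1000 enters Phase II with no reduction.

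**Step 3, does another rule close the gap before treatment?** Exclusion 15 allows the investigator to refuse any unsuitable patient, but it is discretionary. Section 6.3 requires drug-attributed non-hematologic toxicity of grade 3 or higher to have resolved before a cycle starts; it does not require a lower dose. Section 6.1 permits rounding down to tablet size, which is not a dose level.

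**Step 4, what acts during treatment?** Capecitabine is interrupted at hand-foot syndrome of grade 2 or higher (Table 6) and may be reduced after the first grade 2 episode (Table 10, footnote 1). Both drugs are interrupted for diarrhea of grade 2 or higher that lasts more than 7 days despite optimal care (Table 4). These rules can act below the severity of the earlier event, but each needs toxicity to reappear first.

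**Step 5, how many patients?** Exclusion 18 screens 30/36 = 83% of the Phase II set; the other 6/36 = 17% were screened under exclusion 17. The documents do not say how common this history is. As an assumption, for scale only, 0%, 5% or 10% of 30 gives 0, 1.5 or 3 patients.

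**Step 6, the reduced start.** Table 8 level -1 is 1500 mg/m²/day; 1500/2 = 750 mg/m² BID, and 750/1000 = 75%, or 25% below the failed dose. Table 8, footnote 2 allows level -3 when the start is below 2000 mg/m²/day, so two further reductions (1250, then 1000 mg/m²/day) remain.

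**The case against.** The strongest reply is that the split is intended. Two separately numbered, phase-labelled exclusions, identical except for the threshold and repeated in the eligibility form, do not look like a slip. A plausible motive, which the protocol does not state, is that Phase I decides on first-cycle dose-limiting toxicity in cohorts of 3 to 6. Patients prone to capecitabine toxicity could distort that decision, whereas Phase II can manage toxicity by dose reduction. This stands as an explanation of the stricter Phase I rule. It does not justify full-dose re-exposure in Phase II without mitigation.

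The early-acting rules in Tables 4, 6 and 10 also stand, and they reduce the risk materially for hand-foot syndrome. They help less with diarrhea of rapid onset.

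Stronger readings are tempting but not supported:

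- *That the patient repeats a failed regimen with a drug added.* The exclusion does not say that the earlier intolerance occurred on capecitabine alone. Section 2 notes that capecitabine is also given with other chemotherapy, so the earlier regimen may have been a different combination. What repeats is the capecitabine dose.
- *That nintedanib would worsen any of the listed toxicities.* Section 1.8.2 calls the drugs' major side effects distinct and names overlap only for gastrointestinal and liver toxicity. Hand-foot syndrome is not named.
- *That the exclusion contradicts the dose-reduction tables.* Those tables govern toxicity on study, not eligibility.

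**Conclusion.** The gap is real, narrow and minor. Exclusion 18 omits one dose value, and that value is the Phase II starting dose. A patient with documented severe intolerance there can be given 100% of the dose not tolerated before. The barrier before treatment is the investigator's discretion, and the rules during treatment respond only to recurrence.

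Confidence is high on the wording and the dose arithmetic. The clinical size is unknown: the number of such patients is not given and may be zero, and the 0 to 3 shown above is an assumption. The conclusion also assumes that the thresholds are applied literally; Appendix A says no exceptions to eligibility criteria are granted.

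A reader might infer that the Phase II efficacy result is compromised. The documents do not support that. The PFS endpoint, n=36, alpha, power and the decision rule are unchanged.

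**What to change.** Make the threshold in exclusion 18 inclusive (≤1000 mg/m² BID) in section 5.2 and in the eligibility form, so that it matches exclusion 17. This is one phrase in two places, with IRB approval before it takes effect (section 15.1). The downside is possibly a few fewer eligible patients.

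If the sponsor means to admit these patients, give the reason and add to section 6.2 a capecitabine start at Table 8 level -1 (750 mg/m² BID) for them. Also state whether they count among the 36, since they would not be starting at the recommended Phase II dose. This option costs a short addition to section 6.2.
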